## **6 STUDY DRUG/TREATMENT SUPPLY**

### **6.1 FibroGen Investigational Product**

FG-3019 is a fully human IgG1 kappa monoclonal antibody that binds to CTGF. It will be administered at a dose of 30 mg/kg by IV infusion in a total volume of 250 mL (up to 400 mL if necessary) normal saline every 3 weeks. The maximum dose of FG-3019 will be capped at 3,900 mg. Labels will be prepared in accordance with Good Manufacturing Practice and local regulatory guidelines. The labels will fulfil Good Manufacturing Practice Annex 13 requirements for labelling. Label text will be translated into local language.

The patient emergency contact details will not be on the label, but can be found in the informed consent.

#### **6.1.1 Formulation**

FG-3019 is supplied in single-use glass vials containing 10 mL of a sterile, preservative-free solution. The solution is composed of 10 mg/mL FG-3019, 1.60 mg/mL l-histidine, 3.08 mg/mL l-histidine HCl, 8.01 mg/mL sodium chloride and 0.05 mg/mL polysorbate 20, resulting in a solution with a tonicity of approximately 290 mmol/kg and a pH of 6.0.

### **6.2 Reference Therapy (Placebo)**

Placebo (identical to the FG-3019 vehicle) is handled and administered in a manner that is identical to FG-3019.

#### **6.2.1 Formulation**

Placebo is a sterile, aqueous solution of pH 6.0 for dilution into 0.9% serum chloride injection USP prior to IV infusion. The solution formulation contains 8.01 mg/mL sodium chloride, 3.08 mg/mL L-histidine HCL, 1.60 mg/mL L-histidine, and 0.05 mg/mL polysorbate 20. The solution is free of preservatives as the content of each vial is intended for single use. Each vial delivers a nominal volume of 10 mL.

### **6.3 Preparation of Dose and Administration**

The dose of Study Drug (FG-3019 [30 mg/kg] or placebo) for each infusion will be based on the Day 1 weight for the first 12 weeks. Total volumes of <250 mL must be diluted in 0.9% Sodium Chloride Injection according to the Dose Preparation Instructions in the Study Reference Manual. Total volumes of >250 mL FG-3019 can be infused undiluted. The dose should be prepared in a volume of fluid that does not exceed 400 mL. Study Drug will be administered as soon as possible after release from the site's pharmacy and within 8 hours of preparation. Study Drug will be administered by IV infusion, using an infusion set with a sterile, nonpyrogenic, low-protein-binding in-line filter (0.2-micron pore size).

The first administration of Study Drug in any given subject in the Randomized Treatment Period as well as the Extended Treatment Period shall be completed in approximately 2 hours. If the first administration is well tolerated and no drug-related AEs are observed during the infusion or subsequent 1-hour observation period, the second administration of Study Drug shall be completed in approximately 1 hour. All subsequent infusion periods, including those in the Extended Treatment Phase, may be shortened to approximately half an hour. If a drug-related AE occurs during the first or a subsequent infusion, Study Drug will be administered over

approximately 1 hour for the next three infusions. If no drug-related AEs are observed in any of these three infusions, the duration of infusion may be decreased to approximately half an hour.

A physician must be immediately available during the first Study Drug infusion and observation period for each subject. If a subject has a significant infusion reaction, the infusion rate may be slowed or temporarily stopped, depending on the severity of symptoms. If a subject experiences a significant infusion reaction and continues Study Drug dosing, a physician should be immediately available during all subsequent infusions and observation periods. If the Investigator wishes to use premedication, e.g., antihistamines, nonsteroidal anti-inflammatory drugs (NSAIDs) for a subsequent infusion, this should be discussed with the FibroGen Medical Monitor or designee. Infusions are to be continued until the total volume of the infusion has been administered. Subjects will remain at the study site for 1 hour after the end of the infusion for clinical observation. The post-infusion observation period may be reduced to 30 minutes if the subject has had no infusion-related AEs after three infusions. The IV line should remain in place and maintained per site procedures until the end of this post-treatment observation period.

Study Drug will be administered at a hospital or ambulatory setting with adequate facilities for managing medical emergencies. Medications for the treatment of acute reactions, including anaphylaxis, must be available to study site staff for immediate use. There is no specific treatment for an FG-3019 overdose or infusion reaction. Signs and symptoms should be managed with appropriate standard of care treatment.

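### After a drug-related AE during the 2-hour first infusion, Section 6.3 still plans the next infusion over about 1 hour, and it writes no default for an AE seen only in the observation hour

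*Protocol*

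**What the plan says.** Protocol Section 6.3 sets the first infusion in both the Randomized and the Extended Treatment Period at about 2 hours. Section 4.2.3 repeats this for the first extension dose. Two rules in Section 6.3 govern what follows.

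- **Tolerability rule.** If the first administration is well tolerated and "no drug-related AEs are observed during the infusion or subsequent 1-hour observation period", then "the second administration of Study Drug shall be completed in approximately 1 hour". Infusions after that may be cut to about half an hour.
- **Adverse-event rule.** It begins "If a drug-related AE occurs during the first or a subsequent infusion, Study Drug will be administered over" and specifies "approximately 1 hour for the next three infusions". It goes on: "If no drug-related AEs are observed in any of these three infusions, the duration of infusion may be decreased to approximately half an hour".

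The same section has provisions for a significant infusion reaction: "the infusion rate may be slowed or temporarily stopped, depending on the severity of symptoms", and, if dosing continues, "a physician should be immediately available during all subsequent infusions and observation periods". Premedication is to be discussed with the Medical Monitor. On observation time it says: "The post-infusion observation period may be reduced to 30 minutes if the subject has had no infusion-related AEs after three infusions". Section 8 requires removal from treatment when AEs make further participation a risk.

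**The concern.** The tolerability rule treats the move from 2 hours to 1 hour as something the subject earns by getting through the first infusion and the observation hour without a drug-related AE. The adverse-event rule names the first infusion explicitly and then gives the 1-hour infusion anyway. For an AE during the first infusion, the tolerability condition therefore has no effect on infusion 2.

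The two rules also use different triggers. The first counts the infusion and the observation hour as separate intervals; the second counts only the infusion. An AE confined to the observation hour fails the first rule without meeting the second.

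What is at stake is the safety of individual subjects at their second infusion. That includes former placebo subjects, whose first exposure to FG-3019 is at Day 1-EX. No efficacy endpoint, estimate or error rate depends on it.

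**Working it through.** **Inputs.** Dose 30 mg/kg, capped at 3,900 mg (Section 4.5). Durations of about 2, 1 and 0.5 hours (Section 6.3). Sixteen infusions in the randomized phase (Section 4.2.2). As a check on the dose inputs, 30 mg/kg × 130 kg (the weight limit in Section 5.2) = 3,900 mg, which matches the cap. The plan states no infusion rate, so there is no stated rate to reproduce.

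**Planned rate = dose / duration.**

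- 2 h: 30 / 2 = 15 mg/kg/h (3,900 / 2 = 1,950 mg/h at the cap)
- 1 h: 30 / 1 = 30 mg/kg/h (3,900 mg/h at the cap)
- 0.5 h: 30 / 0.5 = 60 mg/kg/h (3,900 / 0.5 = 7,800 mg/h at the cap)

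**Effect of the 1-hour response, by the infusion at which the AE occurs.**

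| AE during an infusion of | Rate then | Next planned rate | Ratio |
|---|---|---|---|
| 0.5 h | 60 | 30 | 0.5 |
| 1 h | 30 | 30 | 1.0 |
| 2 h | 15 | 30 | 2.0 |

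The response slows the next infusion after an AE at the fastest rate and leaves it unchanged after an AE at the middle rate. Only after an AE at the slowest rate does it leave the next infusion faster.

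**First six infusions as written.**

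- No AE: 2 + 1 + 0.5 + 0.5 + 0.5 + 0.5 = 5.0 h
- Drug-related AE during infusion 1: 2 + 1 + 1 + 1 + 0.5 + 0.5 = 6.0 h

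Infusion 2 is the same in both rows. The AE changes only infusions 3 and 4, which stay at 1 hour.

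**AE only in the observation hour.**

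- Tolerability rule: its condition fails, so the 1-hour second infusion is not authorised.
- Adverse-event rule: its trigger is an AE during an infusion. The preceding sentence names the observation period separately, so the literal trigger is not met.
- The half-hour provision covers infusions after the second, so it does not set infusion 2.

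The faster step is withheld, and staying at 2 hours is the natural consequence, but the text does not say so.

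**Who falls under the rule.** About 136 / 2 = 68 subjects receive their first FG-3019 on Day 1. With the 10% dropout assumed in Section 10.1, and if every remaining placebo subject accepts the extension, 68 × 0.9 ≈ 61 more do so at Day 1-EX. That makes at most about 129 first exposures. The documents give no rate of drug-related AEs at first infusions, so I give no expected number of affected subjects.

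**The case against.** The strongest reply is that the step from 2 hours to 1 hour is planned for everyone, so the AE does not cause it. On this view the adverse-event rule is a restriction: it withholds the half-hour infusion until three 1-hour infusions have passed without a drug-related AE. Its trigger has no severity threshold, so it also catches trivial events. Serious cases are covered by slowing or stopping the infusion, physician presence, premedication and, under Section 8, removal from treatment. Section 1.5 reports that infusions were well tolerated and that none was stopped for an AE. Section 11.3.4 sets a demanding standard for calling an AE drug-related, and 1 hour is still half the routine half-hour rate. The Study Reference Manual, which is not among the documents, may add detail.

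Most of this stands, and it limits the size of the point. It does not remove the contradiction. None of these provisions sets the duration of the next infusion. Slowing or stopping, and physician presence at later infusions, are tied to a significant reaction, so a subject with a lesser drug-related AE is simply planned for 1 hour. Section 6.3 cites the manual for dose preparation, not for infusion duration.

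A reader might also infer that sites are left to choose any duration after an observation-hour AE. The text does not support that: it already withholds the 1-hour step, and only the default is unwritten.

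**Conclusion.** The point holds as a minor, low-cost safety correction. For an AE during a 2-hour infusion, Section 6.3 defeats its own tolerability condition: infusion 2 is planned at 30 mg/kg/h after an AE at 15 mg/kg/h, exactly as if no AE had occurred. For an AE seen only in the observation hour, the default of staying at 2 hours should be written down.

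This rests on a literal reading of Section 6.3, on durations that the protocol calls approximate, and on the manual not already resolving the matter.

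Two stronger readings are tempting and not supported. One is that the rule exposes subjects to demonstrable harm: the documents show no dependence of FG-3019 reactions on infusion rate, and they give no AE rate from which a likelihood could be calculated. The other is that the AE trigger is faulty at every infusion: no defect is shown for AEs at 1-hour or half-hour infusions, where the present response never speeds up the next infusion.

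**What to change.** Amend Section 6.3 only for the infusion that follows a 2-hour infusion (Day 1 or Day 1-EX):

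1. If a drug-related AE occurs during the 2-hour infusion or its observation period, give the next infusion over about 2 hours.
2. Step to about 1 hour only after a 2-hour infusion and observation period free of drug-related AEs.
3. Then require three 1-hour infusions free of drug-related AEs before the half-hour infusion.

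The sequence becomes 2, 2, 1, 1, 1, 0.5 h. Leave the present 1-hour rule and its trigger unchanged for AEs at 1-hour or half-hour infusions. Apply the change identically in both arms, so the blind is unaffected.

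**Cost.** Over six infusions: 2 + 2 + 1 + 1 + 1 + 0.5 = 7.5 h against 6.0 h as written after an AE during infusion 1. Over sixteen: 2 × 2 + 3 × 1 + 11 × 0.5 = 12.5 h against 2 + 3 × 1 + 12 × 0.5 = 11.0 h. Either way this is 1.5 extra infusion hours for an affected subject who tolerates the repeat, and more if AEs recur. No visits or procedures are added. The text change is short, but Section 13.2 requires written IRB approval before an amendment is used and Section 4.2 plans about 60 centers. It is best carried in the next amendment, with the Study Reference Manual aligned if it repeats the rule.

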**The following procedures must be performed during each infusion:**

Vital signs (blood pressure [BP], pulse, respiration rate, and temperature) every 30 minutes ( $\pm$  10 minutes)

Query subject and assess AEs and SAEs

Record concomitant medications, including any pre-medication pre-approved by the FibroGen medical monitor or designee

**The following procedures must be performed after each infusion:**

Vital signs (BP, pulse, respiration rate, and temperature) every 30 minutes ( $\pm$  10 minutes) for a minimum of 30 minutes after completion of the infusion (see above)

Query subject and assess AEs and SAEs

Record concomitant medications

## **6.4 Storage**

Vials of Study Drug must be stored refrigerated (2°C to 8°C), temperature-controlled and monitored, protected from light and in a securely locked area to which access is limited to appropriate study personnel. Documentation of the storage conditions must be maintained by the site for the entire period of study participation.

## 7 STUDY PROCEDURES-ALL COHORTS UNLESS OTHERWISE SPECIFIED

### 7.1 Study Procedures

The study procedures and assessments are presented for the Randomized Treatment phase in Appendix 1, for the Extended Treatment phase in [Appendix 2](#), and for End-of-Treatment and Follow-up periods in Appendix 3. See the Study Reference Manual for additional details.

The treatment period in the Randomized Treatment Phase begins on Day 1 (first infusion of Study Drug) and continues through Week 48. Visit windows are within  $\pm 3$  days of the scheduled visit date for Weeks 3 through 48.

After completion of Week 48 assessments and reporting of all AEs, subjects may be eligible to continue to open label treatment in the Extended Treatment Phase. All other subjects undergo the EOS assessments.

Eligible subjects from the Randomized Treatment Phase of the study are offered participation in the Extended Treatment Phase as described under Section [4.2.3](#) and illustrated in [Figure 1](#). A Transition Period of up to 3 weeks between the Week 48 Visit in the Randomized Treatment Phase and Day 1-EX in the Extended Treatment Phase is provided in order to determine subject eligibility for the Extended Treatment Phase and to arrange scheduling of the Day 1-EX Visit. The total interval between the Week 45 Visit in the Randomized Treatment Phase and the Day 1-EX Visit in the Extended Treatment Phase should not exceed 6 weeks. If necessary, an unscheduled visit should be performed to obtain repeat pulmonary function tests (FVC) if the interval between the Week 45 Visit in the Randomized Treatment Phase and the Day 1-EX Visit in the Extended Treatment Phase is expected to exceed 6 weeks.

The treatment period in the Extended Treatment Phase begins on Day 1-EX (first infusion of FG-3019) and continues until progression or withdrawal. Visit windows are within  $\pm 3$  days of the scheduled visit date.

### 7.2 Serial PFT and HRCT

The key study procedures that measure efficacy are serial PFT measurements to look at spirometry (see Procedure Manual for PTF for additional details) and serial HRCT assessments to look for fibrosis (see Site Manual for HRCT and Appendix 5).

### 7.3 Blood Volume

The total amount of blood taken is approximately 13 tablespoons (195 ml) in the Randomized Treatment Phase and 10 tablespoons (150 ml) per year in the Extended Treatment Phase (total 23 tablespoons (345ml) for two years). Subjects who continue Extended Treatment beyond one year will give approximately 150 mL of blood per year.

### 7.4 Missed Visits

Every attempt should be made to complete all study visits within window as outlined in the Schedule of Assessments ([Appendix 1](#), [Appendix 2](#), and [Appendix 3](#)).

Scheduled visit dates are determined from the time of the first dose, which is defined as Day 1. Protocol-defined visits conducted outside the  $\pm 3$  day study visit window will be recorded as a protocol deviation unless there is an AE/SAE/intercurrent illness. If a dose is delayed due to an AE/SAE/illness, the next dose should occur as soon as possible when the patient is stable so that

the dosing interval is close to 3 weeks. No subject should receive more than one dose in any 7-day period. Missed doses are not to be made up through undertaking extra visits. If a subject misses more than two infusions in any 18-week period throughout the study, or two sequential infusions, the FibroGen Medical Monitor should be notified. Subjects who miss three sequential doses or more than one instance of two sequential doses will not be allowed to continue in the study and will be terminated early. The reason for missed doses should be documented in the subject's clinical record.

For missed visits without an AE/SAE/intercurrent illness, the subject will be asked to resume the planned visit schedule and return for the next scheduled visit. If the subject is unable to perform PFTs at a scheduled visit the PFT can be performed at the next scheduled visit.

Refer to the case report form (CRF) completion guidelines in the Study Reference Manual for additional information on CRF completion requirements for missed visits.

## **7.5 Unscheduled Visits**

Unscheduled Visit assessments may be required at the discretion of the Investigator. These should be recorded on the appropriate CRF.

Subjects who, in the judgment of the PFT technician or investigator, are unable to perform PFTs adequately on a scheduled visit should undergo PFT assessment at the next scheduled visit or sooner if feasible.

## **7.6 Assessments**

### **7.6.1 Central Laboratory**

All laboratory tests of blood and/or urine specimens will be performed by a central laboratory or FibroGen, as appropriate. A Central Laboratory Manual with instructions on specimen collection, processing, storing, and shipping to the central laboratory will be provided to all participating sites.

### **7.6.2 Local Laboratory(s)**

A local laboratory will analyze urine (and blood, if necessary) samples for pregnancy testing only.

### **7.6.3 Other Reference Laboratories**

Human anti-human antibody plasma level measurement will be performed at a specialty laboratory.

### **7.6.4 Exploratory Biomarkers**

Serum and plasma samples will be stored and used to explore additional biomarkers of FG-3019's effects. The final selection of these biomarkers will be made by FibroGen, based upon the best scientific data available at that time.

### **7.6.5 DNA for Genomic Analysis**

Fingerlin et al performed a genome-wide association study in subjects with fibrotic idiopathic interstitial pneumonias (N = 1616) and controls (N = 4683) (Fingerlin, 2013) and determined an association of disease with TERT and MUC5B on chromosomes 5p15 and 11p15, respectively, the chromosome 3q26 region near TERC, and identified 7 novel chromosome loci. The novel loci include FAM13A (4q22), DSP (6p24), OBFC1 (10q24), ATP11A (13q34), DPP9 (19p13),

and chromosomal regions 7q22 and 15q14-15. Their findings indicate that genes involved in host defense, cell-cell adhesion, and DNA repair contribute to the risk of fibrotic pulmonary disease. In this study, we plan to collect whole blood samples to isolate patient DNA and evaluate the relationship between clinical response to FG-3019 and variants in these specific chromosomal loci.

A whole blood sample will be collected for DNA analysis on Day 1 before dosing or at subsequent visits for subjects already enrolled in the study who agree to DNA analysis. This testing is optional, requires specific consent by participating subjects and subjects may refuse DNA testing. Only tests for genetic loci associated with IPF will be performed and all samples will be destroyed after testing is completed.

## 8 SUBJECT DISCONTINUATION

Subjects who discontinue the study early should be strongly encouraged to complete the End-of-Treatment and Follow-up Visit ([Appendix 3](#)).

Subjects may withdraw from the study at any time for any reason, whether during the Screening, Treatment, or Follow-up Periods. Completion of efficacy assessments as outlined in [Appendix 3](#) is discretionary and must be discussed in advance with the FibroGen Medical Monitor.

The Investigator must remove a subject from study treatment for the reasons below. Removing a subject from study treatment is based on the judgment of the Investigator in consultation with the FibroGen Medical Monitor.

- Pregnancy in a female subject
- AEs, SAEs, repeated hospitalizations, or medical conditions that make further participation in the study a risk to the subject.
- Clear evidence of progression of IPF and or absolute decline in FVC % of predicted value of  $\geq 10\%$  in the absence of an intercurrent illness, documented by two consecutive spirometry tests.
- Receipt of a prohibited medication that cannot be discontinued.

Dosing may be temporarily suspended up to 4 weeks for:

- Acute exacerbation of IPF, defined as (1) worsening or newly developed dyspnea as reported by the subject ( $\leq 30$  days); (2) new bilateral ground-glass opacities on HRCT superimposed on the UIP abnormalities that defined subject eligibility for the study (Section 5.1); and (3) worsening hypoxemia (in the judgment of the Investigator), in the absence of pulmonary infection, heart failure, or other identifiable causes for this finding.
- Any other intercurrent illness that temporarily precludes the subject receiving the study drug infusion.

The reasons for suspension of treatment should be clearly documented in the subject's clinical record.

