### **4.2.4 End of Treatment and Follow-up**

#### **4.2.4.1 Randomized Treatment Phase**

- Subjects assigned to either FG-3019 or placebo who discontinue treatment before week 48 should undergo end of treatment and safety assessment visits (Appendix 3).
- Subjects who were assigned to FG-3019 complete 48 weeks of treatment and are not going on to the Extended Treatment Period should undergo a Safety Assessment visit (Appendix 3); Week 48 evaluation is identical to End of Treatment visit. Thus, subjects who complete Week 48 and are not eligible for the extension study only need the final safety assessment. Subjects who enter the Extended Treatment Period do not need a final safety assessment because they are continuing treatment).
- Subjects who were assigned to placebo who complete 48 weeks of treatment but do not enter the Extended Treatment Period should undergo a safety assessment as described in Appendix 3.

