#### **10.3.4.1 Primary Efficacy Analysis**

The primary analysis will be to compare the treatment arms in change from baseline to Week 48 in FVC % predicted based on the FAS Population. A rank ANCOVA model will be used, with baseline FVC % predicted value as covariate, treatment group, stratification, and treatment by stratification interaction as fixed effects. Factors may be eliminated from the model if they are insignificant. If the interaction term is significant, the primary analysis will be based on the subgroup of subjects on first-line therapy.

The ranks of the primary endpoint will be based on observed data and on imputed data if observed data are not available. A detailed description of the rank assessment will be described in the statistical analysis plan. A repeated measures model utilizing all observed data will be used for sensitivity analysis.

Descriptive summaries of the primary efficacy parameter will include the following:

1. Median change from baseline by treatment and visit
2. % of subjects with no decline by treatment and visit
3. % of subjects with decline  $\geq 10\%$  by treatment and visit

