- a Screening Visit 2 may be combined with Screening Visit 1.
- b Height will be measured only once at Screening Visit 1. Weight will be measured every 12 weeks to determine dose for the subsequent 12-week interval.
- c Including chest auscultation
- d Spirometry (DLCO at first screening test only).
- e Spirometry
- f Pregnancy tests (performed at Screening Visit 1, pre-dose Day 1, and pre-dose at other times) for women of childbearing potential only: serum pregnancy test at Screening Visit 1; urine pregnancy tests at other visits. A positive urine pregnancy test must be confirmed by serum HCG.
- g See Section 11.3.1 for follow-up of AEs.
- h Refer to Section 4.6.1 for prohibited concomitant medications.
- i Vital signs (blood pressure, pulse, respiration rate, and temperature) must be recorded prior to each FG-3019 infusion. Intra-infusion and post-infusion assessments will be performed according to Section 6.3.
- j Subjects who do not complete all visits in the Treatment Period will be encouraged to return for the assessments listed in Appendix 3.

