### Appendix 3. Schedule of Assessments – Early Termination/End of Treatment and Follow-up Visit

Assessment	Early Termination/End of Treatment a	End of Study
1. SGRQ	X b	
2. Vital Signs	X b	X
3. Complete Physical Exam	X b	
4. Spirometry	X b,c	
5. CBC with Differential	X b	
6. Serum Chemistry	X b	
7. Spot Urine for Urinalysis	X b	
8. Pregnancy Test d	X b	X
9. HRCT of Chest	X b	
10. 12-Lead ECG	X b	
11. Serum and Plasma Biomarkers	X b	
12. Plasma HAHA		X
13. AEs and SAEs e	X b,e	X b,e
14. Concomitant Medications f	X b	X
15. Procedures and Nondrug Therapies	X b	X
16. Subject Disposition	X	X

Abbreviations: AE = adverse event; CBC = complete blood count; ECG = electrocardiogram; HAHA = human anti-human antibody; HCG = human chorionic gonadotropin; HRCT = high resolution computed tomography; PFT = pulmonary function test; SAE = serious adverse event; SGRQ = Saint George's Respiratory Questionnaire.

- a End of treatment, including due to withdrawal/progression evaluation preferably 3 weeks after last dose of study drug for all subjects who have received more than 4 doses of FG-3019. The End of Study, final safety assessment should be 4 weeks after last dose of study drug. Study windows are  $\pm$  3 days
- b Subjects who completed the withdrawal/progression evaluations at Week 48 or for early withdrawal do not need to repeat them. Study endpoint evaluations do not require repetition if performed within 8 weeks, HRCT does not require repetition if performed within 4 months, and safety assessments, such as clinical laboratory tests, do not require repetition if performed within 2 weeks.
- c Spirometry .
- d Pregnancy tests for women of childbearing potential only: urine pregnancy tests at all Extended Treatment Period visits. A positive urine pregnancy test must be confirmed by serum HCG.
- e See Sections 4.7 and 11.3.1 for follow-up of AEs.
- f Refer to Section 4.6.1 for prohibited concomitant medications.

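### No Week 48 FVC is scheduled after early treatment stop, so some outcome-related primary values will be imputed; the modelled effect on the rank test is small, and the gain from measuring is interpretability

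*Protocol*

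**What the plan says.** - **Endpoint and analysis.** Protocol 3.2.1 sets the primary endpoint at Week 48. Protocol 10.3.4.1 analyses it by rank ANCOVA in the Full Analysis Set: "The ranks of the primary endpoint will be based on observed data and on imputed data if observed data are not available". Protocol 10.3.4 leaves the imputation rule to the SAP. SAP Section 1 places the randomised period in Part 1, which was not supplied.
- **Visits.** Appendix 1 has spirometry at Weeks 12, 24, 36 and 48. Its footnote j redirects those who fall out: "Subjects who do not complete all visits in the Treatment Period will be encouraged to return for the assessments listed in Appendix 3".
- **End-of-treatment visit.** Protocol 4.2.4.1 says that subjects in either arm "who discontinue treatment before week 48 should undergo end of treatment and safety assessment visits". Section 8 says that completing the Appendix 3 efficacy assessments "is discretionary and must be discussed in advance with the FibroGen Medical Monitor". Appendix 3 footnote a places the evaluation "preferably 3 weeks after last dose of study drug for all subjects who have received more than 4 doses of FG-3019", and footnote b adds: "Study endpoint evaluations do not require repetition if performed within 8 weeks". The later End of Study visit has no spirometry.
- **Grounds for stopping.** Section 8 lists "Clear evidence of progression of IPF and or absolute decline in FVC % of predicted value" of at least 10, on two consecutive tests, with this qualification: "Removing a subject from study treatment is based on the judgment of the Investigator in consultation with the FibroGen Medical Monitor". Section 7.4 ends study participation, not only treatment, for certain patterns of missed doses.
- **Assignment used.** Protocol 10.3.1 summarises efficacy as well as safety by treatment actually received. Protocol 10.2.1 gives that rule for safety only.

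**The concern.** A gap in the primary variable that is partly triggered by the primary variable is the kind of missingness an imputation rule handles least well. The protocol expects a Week 48 decline of 7.0 on placebo and 2.8 on FG-3019 (10.1), so confirmed falls, and the removals that may follow, should be commoner on placebo. For those subjects the primary rank would come from a rule rather than a measurement, although many could still attend spirometry. A reader of the result could not tell how far it depended on that rule.

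Two smaller matters sit beside this. Sites are told three different things about who has end-of-treatment spirometry. Footnote a counts doses of FG-3019, which sites blinded under 4.4.2 cannot do and which, read literally, leaves out placebo subjects. Separately, summarising efficacy by treatment received would part from randomisation if any subject received the wrong treatment.

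**Working it through.** **1. The plan's own figure.** Inputs from Protocol 10.1: 55 per arm, 10% dropout, SD 7.3, difference 4.2, two-sided 0.05.

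- n = 55 × 0.9 = 49.5 per arm.
- Noncentrality = 4.2 / (7.3 × √(2/49.5)) = 2.86.
- Power = 0.809 (noncentral t), or 0.817 (normal approximation).

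The stated 80% reproduces. The sample size already allows for 10% without data.

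**2. Is there any route to a Week 48 FVC?** Footnote j and 4.2.4.1 both lead to Appendix 3. Its spirometry falls at about week w + 3, where w is the week of the last dose, so the gap to Week 48 is 48 − (w + 3):

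- w = 12: 33 weeks
- w = 24: 21 weeks
- w = 36: 9 weeks

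Footnote b can make the last value older still. Protocol 4.2.2 and 10.3.6 treat a subject as finished on completing Week 48 or discontinuing. No section asks an early stopper to return at Week 48.

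**3. How many.** At the protocol's 10%, 110 × 0.10 = 11 first-line subjects, or 136 × 0.10 = 13.6 overall. An assumed 5–20% gives 5.5–22 of 110. Deaths and withdrawn consent cannot be recovered by scheduling a visit.

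**4. FVC-driven removals.** The documents give no longitudinal data, so these are model assumptions.

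- Change at each visit = subject slope × time + visit error − baseline error.
- Week 48 means −7.0 and −2.8, SD 7.3; visit-error SD σ = 2, 3 or 4.
- Slope SD over 48 weeks = √(7.3² − 2σ²) = 6.73, 5.94 or 4.61.
- A fall of 10 or more is confirmed either by a prompt repeat or at the next scheduled visit, giving six scenarios.
- Every confirmed fall leads to removal. This is an upper bound, because Section 8 leaves it to judgment.

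Removed before Week 48: placebo 6–16% (3–9 of 55), FG-3019 2–7% (1–4 of 55). Their last FVC is on average 13–21 weeks before Week 48. If only half of confirmed falls lead to removal: 3–8% and 1–4%.

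**5. Effect on the result.** The rank effect is the probability that an FG-3019 subject outranks a placebo subject. In closed form with full data it is Φ(4.2 / (7.3√2)) = Φ(0.407) = 0.658.

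| Handling of removed subjects | Mean difference | Rank effect | Rank-test power |
|---|---|---|---|
| Full data | 4.2 | 0.657–0.659 | 79–80% |
| Last value | 3.7–4.1 | 0.655–0.658 | 77–79% |
| Slope extrapolation | 4.3–4.9 | 0.655–0.658 | 77–79% |
| Worst rank | not defined | 0.655–0.658 | 77–79% |
| Repeated-measures type, observed data | 4.0–4.2 | – | – |

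Last value and slope extrapolation move the mean in opposite directions. All three imputation rules move the rank effect slightly downward, by 0.003 or less, because subjects removed for a large fall rank near the bottom whichever rule is used. With half removed, the means are 4.0–4.1 (last value) and 4.2–4.6 (slope).

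Power is from 3,000 unadjusted Wilcoxon tests per scenario at 50 per arm. The Monte Carlo error is about ±1.5 points (1.96 × √(0.79 × 0.21/3000) = 0.015), so the 1–2 point change is near the noise.

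**6. Measured values are not neutral either.** The same model gives 4.05–4.18 if FG-3019 subjects lose the drug effect after stopping, and 3.9–4.1 if removed subjects start another IPF drug with an assumed effect of 4.2. More crudely, if 10% stop and keep a share r of the effect, the difference is 4.2 × (1 − 0.10 × (1 − r)). This gives 3.99 for r = 0.5 and 3.78 for r = 0. The t-test power with all 55 per arm measured is then 0.811 and 0.768, against 0.849 for r = 1.

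**The case against.** The strongest reply is that little is at stake for the planned test. The primary analysis is a rank ANCOVA, its listed summaries are medians and percentages, and ordinary imputation rules barely alter the ranks of subjects who have already fallen by 10 points. Protocol 10.3.4.1 also has a repeated-measures sensitivity model on observed data, and 10.3.4.3 counts deaths and confirmed falls in the Safety Population. This stands, and it limits the point to interpretability. Neither safeguard supplies an FVC after stopping.

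Second, the clash over end-of-treatment spirometry is partly apparent. Section 4.2.4.1 concerns stopping treatment, while the discretionary wording in Section 8 follows a sentence on withdrawing from the study, when assessments are voluntary anyway. That also stands in part. However, the protocol never separates the two states, both sections point to Appendix 3, and footnote a remains unworkable under blinding.

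Three stronger readings are tempting, and the documents do not support them:

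- **That the primary result is biased in a known direction.** The rule is in SAP Part 1, which was not supplied, and the opposite movements are in means, not ranks.
- **That footnote a denies a visit to anyone with four or fewer doses, who would then leave the Full Analysis Set.** The footnote mainly sets timing and does not say that others have no visit.
- **That the primary test will be run as treated.** Section 10.3.1 speaks of summaries, and 10.3.4.1 of comparing treatment arms.

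**Conclusion.** The gap is real on the text: no Week 48 FVC is scheduled after early stopping, a confirmed fall of at least 10 points is a ground for stopping, and the missing ranks are imputed. For FVC-driven removals the consequence for the primary rank analysis is small: a shift of 0.003 or less in the rank effect and about 1–2 points of power, with mean differences spread over about 3.7–4.9 against 4.2.

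This rests on linear decline, the protocol's means and SD, an assumed visit error of 2–4, removal at every confirmed fall, and an unadjusted rank test in place of the ANCOVA. Removals for adverse events or withdrawn consent were not modelled. The point should be acted on because the remedy is cheap and reduces reliance on imputation, not because a bias has been shown or the trial is threatened. The end-of-treatment passages need reconciling whatever the imputation rule. The as-treated wording is a separate, minor inconsistency, and no size is claimed for it.

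**What to change.** Leave the treatment-stopping rules as they are.

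1. **Follow-up.** In 4.2.4.1, 7.4 and 8, separate stopping treatment from leaving the study. Keep consenting subjects on the existing Week 12, 24, 36 and 48 spirometry schedule. Record IPF drugs started after stopping through Week 48, flag off-treatment values, and use them in a pre-specified sensitivity analysis. The choice of primary estimand stays with the sponsor; step 6 of the working shows why these values should not simply be required in the primary analysis.
2. **End-of-treatment spirometry.** Reconcile 4.2.4.1, Section 8 and Appendix 3 footnote a on who has it, in terms that a blinded site can apply.
3. **Assignment.** In 10.3.1, analyse and summarise efficacy by randomised arm and keep actual treatment for safety, consistent with 10.2.1.

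Cost: one to three existing visits per early stopper; medication recording beyond the End-of-Study visit, where 4.6.1 now stops it; consent wording; and a change to the part of 7.4 that ends study participation. Section 4.6.1 does not address IPF drugs after treatment stops, so some values will follow other therapy. Items 2 and 3 are wording only.
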